4.8.5.2 Pain NRS

Treatment effect for pain in 5 locations (eyes, legs, arms, upper back, and lower back) based on separate NRS change from baseline at the last visit of the RCP will be tested using analyses of covariance models using treatment and baseline pain NRS scores as explanatory variables.

4.8.6 Analysis of Immunogenicity, Pharmacokinetics, and Exploratory Biomarkers

4.8.6.1 Analysis of Immunogenicity

The presence of ADAs to MEDI-551 in serum will be assessed over the duration of the study. Immunogenicity results will be analysed by summarizing the number and percentage of subjects who develop detectable ADA by treatment group. The association of ADA with MEDI-551 concentration, blood B-cell levels, attack rate, and TEAEs may be evaluated.

4.8.6.2 Analysis of Pharmacokinetics

MEDI-551 concentration will be summarized descriptively over visits separated by AQP4-IgG seropositive and seronegative NMO/NMOSD subjects. Individual and mean MEDI-551 concentration versus time data will be plotted by AQP4-IgG seropositive and seronegative subjects. Pharmacokinetic parameters will be estimated using noncompartmental methods. Pharmacokinetic parameters will be listed by subjects and separated by AQP4-IgG seropositive and seronegative NMO/NMOSD subjects and summarized descriptively.

Population PK or PK/PD analysis may be conducted to include the exploratory analysis to identify the covariates that affect MEDI-551 PK in this subject population, or to investigate the relationship between MEDI-551 PK, PD, and response as appropriate.

4.8.6.3 Analysis of Exploratory Biomarkers

AQP4-IgG titer, plasma gene signature change from baseline, and B-cell absolute counts and relative percentage based on baseline will be summarized descriptively by treatment groups.

Additional research data and associated exploratory analyses may be reported separately from the main clinical study report.

4.8.7 Additional Analyses

An exploratory analysis of time to AC-determined NMO/NMOSD attack or rescue therapy without an AC-determined NMO/NMOSD attack during the RCP will be conducted by considering rescue therapy as events of interest as well. Subjects who never experience any AC-determined NMO/NMOSD attack nor receive rescue therapy will be censored for this analysis.

The agreement between site-determined NMO/NMOSD attack and AC- determined NMO/NMOSD attacks will be assessed by Kappa statistic.

An inter- and intra-rater reliability assessment will be performed based on a random selection of all events contributing to the primary analysis.

A shift analysis of the scores from the mRS will be performed.

4.8.8 Data Monitoring Committee

An unmasked independent DMC will perform evaluations of safety and clinical outcome data at specified regular intervals throughout the study and make recommendations to the sponsor regarding further conduct of the study. The DMC will conduct an interim analysis for futility as described in the description of the interim analysis in Section 4.8.10.

The DMC will monitor drop-out and missing primary and secondary outcome data on a case by case basis. In addition, the DMC will assess the thoroughness of the screening for possible NMO/NMOSD attacks and the effectiveness of the masking.

The DMC will receive 'real time' reports of new NMO/NMOSD attacks and will review the adherence of the investigators and AC to the process of attack diagnosis and adjudication.

Additional details will be provided in a separate DMC charter.

4.8.9 Control of Type I Error

The study is designed to strongly control the overall Type I error rate of $\alpha = 0.05$ based on the Bonferroni-based chain procedure (Bretz et al, 2009; Millen and Dmitrienko, 2011). The primary null hypothesis will be hierarchically tested first at $\alpha = 0.05$ in the AQP4-IgG seropositive cohort, and, if significant, it will be further tested in the ITT population at $\alpha = 0.05$. If and only if the treatment group comparison is statistically significant within the ITT population, secondary hypotheses will be tested. Null hypotheses for the 4 key secondary endpoints will follow the same sequential testing strategy as the primary analysis (testing within seropositive subjects first, followed by the ITT population if the comparison within seropositive subjects is statistically significant). Each secondary hypothesis will be initially tested based on the Bonferroni method at $\alpha = 0.05/4 = 0.0125$. If the null hypothesis for a particular secondary endpoint is rejected across both the seropositive and the ITT populations, the Type I error saved will be propagated equally to other non-rejected sets of secondary null hypotheses. The testing procedure will be repeated until all null hypotheses are rejected or no further null hypothesis can be rejected. Details are described in Appendix 11.

4.8.10 Interim Analysis for Futility

An unmasked interim analysis will be conducted for futility assessment by an independent DMC when approximately 50% of the total planned AC-determined NMO/NMOSD attacks occur in this study. The information fraction will be determined by the ratio of the number of observed cases of AC-determined NMO/NMOSD attacks and the planned number of AC-determined NMO/NMOSD attacks. The predictive power will be calculated for the primary efficacy endpoint in the AQP4-IgG seropositive cohort as well as the ITT population based on the empirical trend observed at the interim analysis (Lan et al, 2009). The study may be declared as “futile” if calculated predictive power at interim is $< 20\%$ in both AQP4-IgG seropositive cohort and the ITT population. Details are provided in Appendix 10.

5 ASSESSMENT OF SAFETY

5.1 Definition of Adverse Events

The ICH Guideline for Good Clinical Practice (GCP) E6(R1) defines an AE as:

Any untoward medical occurrence in a patient or clinical investigation subject administered a pharmaceutical product and which does not necessarily have a causal relationship with this treatment. An AE can therefore be any unfavorable and unintended sign (including an abnormal laboratory finding), symptom, or disease temporally associated with the use of a medicinal product, whether or not considered related to the medicinal product.

An AE includes but is not limited to any clinically significant worsening of a subject’s pre-existing condition. An abnormal laboratory finding (including ECG finding) that requires medical intervention by the investigator, or a finding judged by the investigator as medically

significant should be reported as an AE. If clinical sequelae are associated with a laboratory abnormality, the diagnosis or medical condition should be reported (eg, renal failure, hematuria) not the laboratory abnormality (eg, elevated creatinine, urine red blood cells increased). Abnormal laboratory values that are not, in the investigator's opinion, medically significant and do not require intervention should not be reported as AEs.

Adverse events may be treatment emergent (eg, occurring after initial receipt of investigational product) or nontreatment emergent. A nontreatment-emergent AE is any new sign or symptom, disease, or other untoward medical event that begins after written informed consent has been obtained but before the subject has received investigational product.

Elective treatment or surgery or preplanned treatment or surgery (that was scheduled prior to the subject being enrolled into the study) for a documented pre-existing condition that did not worsen from baseline is not considered an AE (serious or nonserious). An untoward medical event occurring during the prescheduled elective procedure or routinely scheduled treatment should be recorded as an AE or SAE.

For the purposes of this protocol, NMO/NMOSD attacks will not be recorded as an AE during either the RCP or the OLP. Symptoms that are subsequently diagnosed due to another underlying cause will be recorded as AEs.

5.2 Definition of Serious Adverse Events

An SAE is any AE that:

- Results in death (for the purposes of this protocol, this includes NMO/NMOSD disease progression or attack)
- Is immediately life-threatening
- Requires inpatient hospitalization or prolongation of existing hospitalization
- Results in persistent or significant disability/incapacity
- Is a congenital anomaly/birth defect in offspring of the subject
- Is an important medical event that may jeopardize the subject or may require medical intervention to prevent one of the outcomes listed above

Medical or scientific judgment should be exercised in deciding whether expedited reporting is appropriate in this situation. Examples of medically important events are intensive treatment in an emergency room or at home for allergic bronchospasm, blood dyscrasias, or convulsions that do not result in hospitalizations; infection that requires treatment with IV antibiotics; or development of drug dependency or drug abuse.

For the purposes of this protocol, NMO/NMOSD disease progression or attack that do not result in death, but meet any of the other above listed SAE criteria, will not be reported as an SAE unless it occurs during the screening period or in the SFP.

NMO/NMOSD disease progression or attacks that result in death will be reported as SAEs.

All occurrences of NMO/NMOSD attacks will be carefully monitored by the site staff and the Sponsor to ensure these are identified in the required reporting timeline.

Additionally, hospitalization for any procedure resulting from an NMO/NMOSD attack will *not* be reported as an SAE (eg, PLEX that could result in hospitalization).

5.3 Definition of Adverse Events of Special Interest

An adverse event of special interest (AESI) is one of scientific and medical interest specific to understanding of the Investigational Product and requires close monitoring and rapid communication by the investigator to the Sponsor. An AESI may be serious or non-serious. The rapid reporting of AESIs allows ongoing analysis of these events in order to characterize and understand them in association with the use of this investigational product.

Two adverse events are considered AESIs for this study: 1) hepatic function abnormality meeting the definition of Hy's law; and 2) PML. See Section 5.6.2 and Section 5.6.3 for the definition and reporting of AESIs of hepatic function abnormality and PML, respectively.

5.4 Recording of Adverse Events

Adverse events will be recorded on the eCRF using a recognized medical term or diagnosis that accurately reflects the event. Adverse events will be assessed by the investigator for severity, relationship to the investigational product, possible etiologies, and whether the event meets criteria of an SAE and therefore requires immediate notification to the Sponsor's Patient Safety designee as described in Section 5.5. See Section 5.2 for the definition of SAEs and Appendix 3 and Appendix 12 for guidelines for assessment of severity and relationship. If an AE evolves into a condition that meets the regulatory definition of "serious," it will be reported on the SAE Report Form.

Infusion of biological products is commonly associated with infusion related reactions. Anaphylaxis and infusion related reactions have some common manifestations and may be difficult to distinguish from each other. Infusion related reactions are commonly observed during or shortly after the first time exposure to therapeutic monoclonal antibodies delivered through intravenous infusion. These reactions are less common following subsequent exposures. Unlike infusion related reactions, anaphylaxis is a rare event, usually occurring after subsequent exposure to an antigen, and it is most commonly accompanied by severe

systemic skin and or mucosal reactions. The investigator is advised to carefully examine symptoms of adverse reactions observed during or shortly after exposure to MEDI-551, and consider the above-mentioned facts prior to making a final diagnosis. Reactions occurring at the time of or shortly after subsequent infusions of investigational product are to be judged by the investigator at his/her own discretion. For the investigator's convenience and in order to facilitate consistency in judgments a copy of the NIAID and FAAN guidance for anaphylaxis diagnosis is provided in Appendix 2.

5.4.1 Time Period for Collection of Adverse Events

Adverse events will be collected from the time of signature of informed consent throughout the treatment periods, including the SFP.

All SAEs will be recorded from the time of informed consent.

5.4.2 Follow-up of Unresolved Adverse Events

Any AEs that are unresolved at the subject's last AE assessment or other assessment/visit as appropriate in the study are followed up by the investigator for as long as medically indicated, but without further recording in the eCRF. The Sponsor (or designee) retains the right to request additional information for any subject with ongoing AE(s)/SAE(s) at the end of the study, if judged necessary.

5.5 Reporting of Serious Adverse Events

Within 24 hours of identifying an SAE, regardless of the presumed relationship to the investigational product, the investigator or qualified designee must complete the SAE Report Form and submit by email to the Sponsor's designated safety reporting address below. The report may be submitted by fax if email is unavailable.

Safety Reporting e-mail address:	PPD [REDACTED]
Fax (if email is unavailable):	PPD [REDACTED]

The Sponsor/designee is responsible for reporting certain SAEs as expedited safety reports to applicable regulatory authorities, ethics committees, and participating investigators, in accordance with ICH Guidelines and/or local regulatory requirements. The Sponsor/designee may be required to report certain SAEs to regulatory authorities within 7 calendar days of being notified about the event; therefore, it is important that investigators submit additional information requested by the Sponsor as soon as it becomes available.

Investigators should provide all available information at the time of SAE Report Form completion. Investigators should not wait to collect additional information to fully document the event before notifying the Sponsor/designee of an SAE. When additional information

becomes available, investigators should submit a follow-up SAE Report Form (separate from the initial report form) with the new information. Any follow-up information to an SAE also needs to be provided to the Sponsor/designee within 24 hours of learning of the new information.

5.6 Other Events Requiring Immediate Reporting

5.6.1 Overdose

An overdose is defined as a subject receiving a dose of investigational product in excess of that specified in this protocol, or receiving investigational product at a time/visit not specified in this protocol.

Any overdose of a study subject with the investigational product, with or without associated AEs/SAEs, must be reported within 24 hours of knowledge of the event to the Sponsor/designee using the Overdose Notification Form and the email address below (or by fax if email is unavailable):

Safety Reporting e-mail address:	PPD [REDACTED]
Fax (if email is unavailable):	PPD [REDACTED]

If the overdose results in an AE, the AE must also be recorded on the AE eCRF (see Section 5.4). Overdose does not automatically make an AE serious, but if the consequences of the overdose are serious, for example death or hospitalization, the event is serious and must be reported as an SAE (see Section 5.4 and Section 5.5). The Sponsor/designee does not recommend specific treatment for an overdose. The investigator will use clinical judgment to treat any overdose.

5.6.2 Hepatic Function Abnormality

Events of hepatic function abnormality of special interest to the Sponsor are defined as any increase in ALT or AST to greater than $3 \times \text{ULN}$ **and concurrent** increase in bilirubin to greater than $2 \times \text{ULN}$ (ie, Hy's law cases). Concurrent findings are those that derive from a single blood draw or from separate blood draws taken within 8 days of each other. In the event of hepatic function abnormality where the etiology is unknown, timely follow-up investigations and inquiries should be initiated by the investigational site, based on medical judgment, to make an informed decision regarding the etiology of the event.

All occurrences of hepatic function abnormality that meet the criteria of Hy's Law are to be considered SAEs and reported to the Sponsor/designee within 24 hours as described in Section 5.5. If the underlying diagnosis for the hepatic function abnormality is known (including progression of pre-existing disease), the diagnosis should be recorded as the SAE.

If the underlying diagnosis for the hepatic function abnormality remains unknown, the term “hepatic function abnormal” should be used to report the SAE.

The investigator will review the data with the medical monitor. The investigator should then use clinical judgment to establish the cause based on local standard of care and follow the subject by conducting testing as clinically indicated.

If, after appropriate workup, in the opinion of the investigator, the underlying diagnosis for the abnormality remains unexplained, or is considered attributable to investigational product, dosing of the study subject should be permanently discontinued.

Each reported event of hepatic function abnormality will be followed by the investigator and evaluated by the Sponsor.

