4.1.6 Discontinuation of Investigational Product

An individual subject will not receive any further investigational product if any of the following occur in the subject in question:

- 1 Withdrawal of consent for further treatment with investigational product or the subject is lost to follow-up
- 2 An AE that, in the opinion of the investigator or the Sponsor, contraindicates further dosing

- 3 Subject is determined to have met one or more of the exclusion criteria or failed to meet all of the inclusion criteria for study participation and there is a potential safety risk associated with continuation identified upon consultation with the medical monitor
- 4 Pregnancy
- 5 Any of the following liver function abnormalities:
 - (a) ALT or AST $> 8 \times$ ULN
 - (b) ALT or AST $> 5 \times$ ULN for more than 2 weeks (in absence of elevated bilirubin and/or other symptoms listed in item 'd')
 - (c) ALT or AST $> 3 \times$ ULN and total bilirubin $> 2 \times$ ULN or international normalized ratio [INR] > 1.5 ; see Section 5.6.2 for additional details regarding reporting of subjects with ALT or AST $> 3 \times$ ULN and total bilirubin $> 2 \times$ ULN with unknown etiology (ie, Hy's law cases)
 - (d) ALT or AST $> 3 \times$ ULN with the appearance of fatigue, nausea, vomiting, right upper quadrant pain or tenderness, fever, rash, and/or eosinophilia ($> 5\%$)
- 6 Any life-threatening (Grade 4) clinical event including anaphylaxis related to the investigational product as agreed upon consultation with the medical monitor
- 7 Recurrent severe (Grade 3) hypersensitivity reaction related to the investigational product as agreed upon consultation with the medical monitor
- 8 Recurrent severe (Grade 3) infusion reaction related to investigational product as agreed upon consultation with the medical monitor
- 9 Grade 3 or higher neutropenia that does not improve to at least Grade 2 within 5 days as agreed upon consultation with the medical monitor
- 10 Receipt of a prohibited medication in the RCP prior to Day 15 or during the OLP following consultation with the medical monitor (see Section 4.7.2).
- 11 Noncompliance to the study protocol as judged by the investigator and/or the Sponsor

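### Protocol Sections 4.1.6 and 5.6.2 give different stopping rules at the same ALT/AST and bilirubin thresholds: one ignores cause, the other depends on it

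*Protocol*

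**What the plan says.** **Protocol Section 4.1.6 (Discontinuation of Investigational Product)** opens with a mandatory sentence: "An individual subject will not receive any further investigational product if any of the following occur in the subject in question". Item 5 of the list is introduced by "Any of the following liver function abnormalities". Its sub-item (c) is ALT or AST above 3 times ULN together with total bilirubin above 2 times ULN or INR above 1.5. Item 5(c) then points elsewhere: "see Section 5.6.2 for additional details regarding reporting of subjects with ALT or AST" above 3 times ULN and bilirubin above 2 times ULN, "with unknown etiology (ie, Hy's law cases").

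**Protocol Section 5.6.2 (Hepatic Function Abnormality)** uses the same ALT/AST and bilirubin thresholds. It calls every case that meets them a Hy's law case and makes each one an SAE. It expects a workup and a review of the data with the medical monitor. It recognises that the underlying diagnosis may be known, including progression of a disease the subject already had, and says how to record such a case. Its dosing instruction is conditional on the outcome of the workup: permanent discontinuation is called for if "the underlying diagnosis for the abnormality remains unexplained, or is considered attributable to investigational product".

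**SAP Section 3.1.3** has a protocol-deviation category for subjects who met a discontinuation criterion but stayed on investigational product. **SAP Section 3.7.1.2** summarises adverse events that led to discontinuation of investigational product.

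**The concern.** A site with a qualifying liver result has two places to look, and for one type of subject they do not lead to the same action. Take a subject whose abnormality is traced to something other than the study drug. Under 4.1.6 that subject receives no more investigational product. Under 5.6.2 the stated condition for permanent discontinuation has not been met.

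At stake are whether that subject is dosed again, whether re-dosing is recorded as a protocol deviation, and whether the event enters the table of adverse events leading to discontinuation. A safety stop written in mandatory terms should not leave sites to choose between two sections.

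**Working it through.** No arithmetic applies: nothing here rests on a sample size, an event count or an error rate. The check is to put one finding through both sections. The finding is ALT or AST above 3 times ULN and bilirubin above 2 times ULN on a single blood draw. The INR alternative appears only in 4.1.6 and is left out of the comparison.

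| Cause after workup | Section 4.1.6, item 5(c) | Section 5.6.2 | Agree? |
|---|---|---|---|
| Unexplained | Stop | Stop | Yes |
| Attributed to investigational product | Stop | Stop | Yes |
| Known other cause | Stop | Stop condition not met; no dosing instruction given | No |

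**Does the cross-reference resolve the third row?** No. Item 5(c) sends the reader to 5.6.2 for reporting details only. The words on unknown etiology belong to that reporting reference and do not limit the stopping threshold.

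**Can a cause qualifier be read into item 5?** Not fairly. Where 4.1.6 wants a qualifier, it writes one. Item 7, for example, reads "Recurrent severe (Grade 3) hypersensitivity reaction related to the investigational product as agreed upon consultation with the medical monitor". Items 6 and 8 likewise require relatedness and medical-monitor consultation, and item 9 requires consultation. Item 5 has neither.

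**Timing.** Item 5(c) takes effect when the finding occurs; the 5.6.2 instruction takes effect only after the workup. In the RCP, Table 6 schedules serum chemistry on Day 8 and the second infusion on Day 15, nominally 15 − 8 = 7 days later. A qualifying Day 8 result rules out the second infusion under 4.1.6. Under 5.6.2 the workup may still be open on Day 15, and that section does not say what happens to the dose. In the OLP, maintenance doses are 26 weeks apart, so a workup will usually be finished before the next dose and the third row becomes a live decision.

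**Hy's law wording.** Section 4.1.6 attaches the term to cases of unknown etiology. Section 5.6.2 attaches it to any case meeting the thresholds, including those with a known diagnosis.

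**Consequence in the SAP.** A subject in the third row who is dosed again under the 5.6.2 reading has, under the 4.1.6 reading, met a discontinuation criterion and continued treatment. That is the deviation category in SAP Section 3.1.3.

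**The case against.** The strongest reply is that the sections do not strictly collide. Section 5.6.2 nowhere says that a subject with a known other cause may be dosed again. It gives a condition for stopping and is silent otherwise, so a site that always follows 4.1.6 breaches neither section. The placement also favours 4.1.6: it is the section on discontinuation and is worded as mandatory, whereas 5.6.2 sits among events requiring immediate reporting and says only that dosing should stop. This stands in part. A reader might infer that such a subject is expressly both barred from and cleared for dosing. The documents do not support that, because the permission arises only by implication. But if 4.1.6 always governs, the cause condition in 5.6.2 does nothing, and neither document states that 4.1.6 governs.

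A reader might also infer that the count of the hepatic adverse event of special interest depends on which section is used. It does not. Protocol Section 5.3 takes the definition from 5.6.2 alone, and that definition contains no test of cause. SAP Section 3.7.1.1 leaves the search criteria for hepatic function abnormality to be set before database lock.

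Existing controls narrow the practical gap. Section 5.6.2 requires review with the medical monitor and evaluation by the sponsor. Section 4.5.3 requires discussion with the medical monitor when a dose is delayed for medical or safety reasons. SAP Section 3.1.3 says the specific deviation criteria will be agreed before unmasking. These make an unreviewed re-dosing less likely and give a point at which the deviation question could be settled. None of them says which stopping rule applies.

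**Conclusion.** The point holds as an inconsistency in a mandatory safety stopping rule. At the same ALT/AST and bilirubin thresholds, 4.1.6 stops dosing whatever the cause and at once, while 5.6.2 ties permanent discontinuation to the cause found after a workup. The divergence is confined to subjects with a known other cause and to doses that fall due while a workup is open. The difference in Hy's law wording is secondary.

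The size is small. The documents give no event rate. Events are likely to be few, partly because screening excludes ALT or AST above 2.5 times ULN and bilirubin above 1.5 times ULN (Gilbert's syndrome excepted). In the RCP only one dose follows Day 1; in the OLP the question can arise at each dosing visit. The primary endpoint, power and alpha are not affected. The effects are on an individual subject's dosing, the deviation listing and the discontinuation table.

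The conclusion rests on two readings: that item 5(c) means what it says without an unwritten qualifier, and that the cause condition in 5.6.2 was meant to have some effect. It takes no view on which clinical rule is right.

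**What to change.** Reconcile item 5(c) of Section 4.1.6 with the dosing sentence in Section 5.6.2 so that one stopping rule is stated, with the other section referring to it. The text should make clear whether meeting the thresholds ends dosing regardless of cause or only after the cause has been determined, and how a dose falling due during the workup is handled. The choice belongs to the sponsor's safety team.

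Align the description of Hy's law cases in 4.1.6 with 5.6.2. Section 5.3 already defers to 5.6.2 and needs no change. When the deviation criteria under SAP Section 3.1.3 are agreed, they should follow the reconciled rule.

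The cost is a sentence or two of protocol wording, with no new tests, visits or analyses.
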